Exclusion criteria – Conditions: BMI > 30 kg/m² (obese are ineligible because anamorelin may cause weight gain); osteoporosis of the spine or hip by DXA scan (specifically, T-score ≤ -2.5 at two lumbar vertebrae or at the total hip or femoral neck, as recommended by the International Society for Clinical Densitometry [ISCD]); current participation in a fitness program or weight loss program; advanced knee osteoarthritis (OA) or other conditions preventing strength or function testing; lower extremity fracture in the last year; diabetics taking insulin or sulfonylureas and subjects with a fasting blood sugar on screening >150 mg/dl; inadequate hepatic function defined as AST and ALT levels > 2 x upper limit of normal at screening (>74 and >68 MU/ml, respectively); untreated thyroid or parathyroid disease; significant immune disorder; eGFR<30 ml/min; any clinically meaningful ECG abnormality on screening or baseline; Crohn's disease; active malignancy or cancer therapy in the last 3 years (except nonmelanoma skin cancer); non-English speaking subjects (we can't be confident that non-English speaking subjects could accurately complete the diet assessments which are critical to the integrity of the study); allergy to components of the study interventions; other condition or abnormality in screening labs at discretion of the study physician (the PI); Medications: osteoporosis treatment – teriparatide, abaloparatide, raloxifene, denosumab, or romosozumab in the last 12 mo or a bisphosphonate in the last 2 years; Tamoxifen in the last 6 mo; since anamorelin is mainly metabolized by CYP3A4, candidates will be excluded if they are taking strong CYP3A4 inhibitors within the previous two weeks (ketoconazole, clarithromycin, itraconazole, nefazodone, telithromycin); use of drugs that may prolong the PR or QRS interval durations, such as any of the Class I/Sodium (Na⁺) Channel blocking antiarrhythmic medications (e.g. flecainide, procainamide, propafenone, quinidine); drugs with high affinity to AAG and therefore with potential to displace anamorelin from binding (e.g., carvedilol, chlorpromazine); inhibitors of P-glycoprotein (e.g., verapamil, quinidine), and inhibitors of OATP1B3 (e.g., cyclosporine, rifampicin); CYP3A4 inducers (e.g., rifampin); oral or IV glucocorticoids (>10 days in the last 3 mo); gonadal hormones (vaginal estrogen okay); drugs to promote weight loss or gain; or TNF- α inhibitors (e.g., adalimumab, adalimumab-atto, certolizumab pegol, etanercept, etanercept-szzs, golimumab, infliximab).

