The Bioinformatics Specialist, [name], will create the one to one randomization allocation for this study using a block randomization stratified by sex. Due to the small sample size, a block size of 4 will be used. At enrollment, subjects will be randomized by a research coordinator using the randomization module in REDCap. When the subject comes for the baseline visit, a research coordinator will notify the TMC pharmacy of the treatment assignment (group A or group B). A research coordinator will pick up the pill bottle from the Pharmacy and give it to the subject. With the exception of the bioinformatics specialist, the study statistician,

and the pharmacist, all study personnel will be blinded to treatment assignment. In the event of an SAE and upon recommendation of the study physician, the bioinformatics specialist will inform the participant's primary care physician of the treatment assignment. The study physician will remain blinded.

H. Data management

Data collected during this single-site study will not leave the site. All data will be entered into electronic data capture (EDC) forms built in REDCap. Primary data records include: EDC forms completed by the research coordinator during subject interviews and physical measurements, electronic database files generated directly by the DXA bone scanning equipment, and electronic database files of biochemical screening tests generated by the Nutrition Evaluation Laboratory.

All electronic data forms will utilize data entry validation for data types and data ranges to minimize potential for error and will undergo monthly data quality checks by a member of the Biostatistics and Data Management Core Unit at the HNRCA to ensure data quality.

The study database and all source data will be maintained on the HNRCA REDCap server for a minimum of 10 years post study completion per the HNRCA data retention policy. Duplicate copies of these data will be maintained on the HNRCA disaster recovery server as well as the Bone Metabolism Laboratory network storage.

Electronic DXA data files are generated by the DXA scanner located in the Bone Metabolism Laboratory. Biochemical data are manually entered by staff of the Nutrition Evaluation Laboratory and transferred into REDCap. Original paper copies of biochemical assay results are kept in the Nutrition Evaluation Laboratory until and beyond the end of all study activity.

I. Study power

Aim 1: Muscle mass by D₃-creatine dilution –

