Secondary aims - With 4 measurements (baseline, 2, 6, and 12 months), we will test whether the change over time is linear with use of linear models with random effects. The observed pattern of change in ALM over time will give an indication of the potential long-term benefit (or lack thereof) of anamorelin treatment. A significance level of 0.05 will be used.

The findings from secondary (and exploratory) analyses will be used for hypothesis generation, rather than to draw conclusions.

Exploratory aims – Exploratory outcomes will be analyzed as described above. For those with more than two measurements, the pattern of change will be analyzed as described above for ALM.

The primary analyses will follow intention-to-treat principles. The intent to treat population will include all subjects who had 1 or more visits after visit 0 (baseline). We will also perform per protocol analyses, in which subjects who develop clinical conditions during the study that influence the study outcomes (i.e., started treatment on an osteoporosis drug or glucocorticoids) or with selected protocol deviations will be excluded. Data will be diagnosed to evaluate validity of model assumptions. Assumptions of normality and homoscedasticity will be evaluated in these models and appropriate variable transformations will be applied if needed to satisfy model assumptions. If model assumptions do not hold for the linear mixed models, robust standard errors will be used. An exploratory per-protocol analysis will also be performed.

Safety and tolerability measures will be summarized for each treatment group based on clinical symptoms and circulating levels of glucose and ALT/AST. Adherence will be assessed by intake diary and pill counts.

K. Withdrawal from the study

Participants can go permanently “off study” only for withdrawal of consent, defined as no longer wishing to participate in all aspects of the trial. The PI may also withdraw participants for safety reasons. Participants can be off of study pills (non-adherent) but remain in the study and return for scheduled follow-up visits. Participants who are instructed by their doctor to gain weight during the study will not be withdrawn from the study.

PROTECTION OF HUMAN SUBJECTS

a. Materials and potential risks

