Anamorelin may cause weight gain. Gains in lean mass and bone mass are the goal, thus weight gain is expected to occur. In a 12-week anamorelin trial in 174 lung cancer patients, anamorelin increased weight by 1.56 kg, in comparison with placebo and most of the gain occurred in the first 3 weeks of treatment (43). Fat mass is also expected to increase, but gains solely in fat mass have not been observed with anamorelin. To set a weight gain limit runs the risk of discontinuing those subjects who have the most favorable responses to treatment. Thus our approach is to set no weight limit but to monitor metabolic state which reflects the metabolic impact of the weight gain. Gains in lean mass are expected to improve glucose tolerance, whereas exclusive or outsized gains in fat mass would increase blood sugar. To address this and to minimize risk, we plan to exclude obese subjects and subjects taking insulin or sulfonylureas and those with fasting glucose levels on screening ≥ 150 mg/dl. To identify intra-study hyperglycemia we will monitor fasting plasma glucose at 2, 6, and 12 months.

Anamorelin at very high doses may lengthen the QT interval. A study in 60 normal adults (see Investigator brochure) revealed that a supra-therapeutic dose of 300 mg/d of anamorelin was associated with a small increase in heart rate as well as increases in the QT and PR intervals and QRS duration. *In contrast, data collected so far indicate that the therapeutic dose of anamorelin (100 mg) had no clinically meaningful effect on heart rate, QT or PR interval, or QRS duration.*

In conclusion, anamorelin was well tolerated and safe in normal adults and in advanced cancer patients most of whom were on chemotherapy and/or radiation regimens. It is highly likely to be well tolerated and safe in generally healthy community-dwelling adults in this study.

Placebo The matching placebo tablets will contain the inert substance microcrystalline cellulose that is not expected to have any adverse effect.

Blood draws Expected risks of a blood draw include slight discomfort on puncturing the skin and possible bruising in the area. Uncommon or rare risks may include phlebitis and/or scarring. The amount of blood to be drawn, 9 ml for the screening tests and 56 ml for the intra-study measures is well within the limit for research participants (maximum allowable is 500 ml over 8 weeks according to the American Red Cross).

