Nonclinical data indicate that the T_{max} in cardiac tissue is delayed compared with plasma T_{max} (4 hrs vs 1 hr, respectively). We will perform a screening ECG and exclude individuals with clinically meaningful abnormalities. We will also perform ECGs before and 1 and 4 hrs after the first dose of the study pills.

Stopping rules

- We will discontinue the subject's participation in the study if the QT interval exceeds 470 ms or if other clinically meaningful ECG changes occur at either 1 hr or 4-hrs post first dose (4 hrs post dose is the time when the anamorelin concentration in cardiac tissue is maximal).
- We will discontinue the subject's participation in the study in the event that he/she develops cardiac symptoms (e.g., chest pain, chest pressure, palpitations) or evidence of significant fluid retention (peripheral edema, pulmonary congestion).
- We will discontinue a subject's participation in the study if he/she is prescribed the following drugs during the study:
 - CYP3A4 inhibitor (ketoconazole, clarithromycin, itraconazole, nefazodone, or telithromycin)
 - Channel blocking antiarrhythmic medication (flecainide, procainamide, propafenone, quinidine)
 - Drugs with high affinity to AAG (carvedilol, chlorpromazine)
 - Inhibitors of P-glycoprotein (verapamil, quinidine)
 - Inhibitors of OATP1B3 (cyclosporine, rifampicin)
- We will discontinue a subject's participation in the study if he/she develops glycemia defined as fasting plasma glucose ≥ 200 mg/dl on two consecutive measures.

Subjects developing these findings or symptoms will be referred to their physicians and these adverse events will be recorded and reported to the IRB, the NIH, and Helsinn Therapeutics. The study physician will follow up with the subject and his/her physician until symptoms have been appropriately addressed.

We will exclude subjects with eGFR < 30 ml/min.

The study will be approved by the Tufts IRB before anyone will be recruited for the study. All study personnel have been certified by the Tufts IRB to work with clinical research participants. All research activity will take place at the HNRCA. Written informed consent will be obtained from each participant.

The PI will inform the IRB of any updated information that may affect the conduct of this study or subject safety, rights, welfare or willingness to take part in the research.

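### The ECG stopping rule puts its 470 ms limit on the QT interval without heart-rate correction, so read literally it is too strict at slow heart rates and too lax at faster ones.

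*Combined protocol and SAP*

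**What the plan says.** The protocol schedules four ECGs: one at screening and three at the baseline visit. On the baseline tracings, the text just above Stopping rules says: "We will also perform ECGs before and 1 and 4 hrs after the first dose of the study pills". No ECG is planned at a later visit.

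The rule itself is mandatory. Participation ends "if the QT interval exceeds 470 ms or if other clinically meaningful ECG changes occur". The second limb, joined by *or*, covers the case that "other clinically meaningful ECG changes occur at either 1 hr or 4-hrs post first dose". No criteria are given for that limb.

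For entry, section C (Exclusion criteria) excludes "any clinically meaningful ECG abnormality on screening or baseline", with no QT figure.

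On the drug's effect, the section on known potential risks says that 300 mg/d raised heart rate slightly and lengthened QT, PR and QRS. It says that 100 mg, the trial dose, "had no clinically meaningful effect on heart rate, QT or PR interval, or QRS duration".

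On timing, section G says: "At enrollment, subjects will be randomized by a research coordinator using the randomization module in REDCap". The enrollment visit is on Day -3, before the first dose. Section J limits the intention-to-treat population to subjects with at least one visit after baseline.

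**The concern.** The QT interval shortens as the heart beats faster and lengthens as it slows. One raw limit therefore means different things at different rates. Taken literally, the rule has two effects.

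- **Slow rate.** A subject with raw QT above 470 ms and corrected QT below it must be removed, even if the tracing has not changed since before the dose. The second limb only adds grounds for removal, so it cannot keep this subject in. Nor does entry screening reliably filter such subjects out, because a long raw QT caused only by a slow rate need not be judged clinically meaningful.
- **Faster rate.** A subject with corrected QT above 470 ms and raw QT at or below 470 ms does not meet the numeric limit. Whether that subject continues depends on an undefined judgement.

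This is the only numeric cardiac trigger in the plan, and these are the only post-dose ECGs before 12 months of dosing. At 300 mg/d heart rate and QT rose together. That is the situation in which a raw reading understates the corrected one.

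A wrong removal also has an analysis cost. The subject has been randomized, but ending participation on Day 0 leaves no visit after baseline, so the subject drops out of the intention-to-treat population in either arm. The design enrolls 32 to keep 24 completers, which allows 32 − 24 = 8 losses, and each unnecessary removal uses one.

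**Working it through.** The limit of 470 ms is stated without a derivation, so there is no figure of the plan's own to reproduce. The check converts raw QT to corrected QT.

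**Inputs**
- Limit: 470 ms (Stopping rules).
- Heart rates of 50 to 80 bpm: my assumption; the documents give none.
- Formulas: my assumption; the documents name none. With RR = 60/heart rate in seconds, Fridericia is QTcF = QT / RR^(1/3) and Bazett is QTcB = QT / RR^(1/2).

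**Step 1. What raw 470 ms means at each rate, and which raw QT would equal a corrected 470 ms (ms, rounded)**

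| Heart rate (bpm) | RR (s) | QTcF at raw 470 | QTcB at raw 470 | Raw QT at QTcF 470 | Raw QT at QTcB 470 |
|---|---|---|---|---|---|
| 50 | 1.200 | 442 | 429 | 499 | 515 |
| 55 | 1.091 | 457 | 450 | 484 | 491 |
| 60 | 1.000 | 470 | 470 | 470 | 470 |
| 65 | 0.923 | 483 | 489 | 458 | 452 |
| 75 | 0.800 | 506 | 525 | 436 | 420 |

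For example, at 50 bpm QTcF = 470 / 1.2^(1/3) = 442.3. At 75 bpm it is 470 / 0.8^(1/3) = 506.3. Raw and corrected limits agree only at 60 bpm.

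**Step 2. Width of the misclassified bands, taking 470 ms as the intended corrected limit (Fridericia)**
- At 50 bpm: 470 × 1.2^(1/3) = 499.4, and 499.4 − 470 = 29.4 ms. Raw values from 471 to 499 ms force removal although QTcF is below 470.
- At 75 bpm: 470 × 0.8^(1/3) = 436.3, and 470 − 436.3 = 33.7 ms. Raw values from 437 to 470 ms miss the numeric limit although QTcF is above 470.

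**Step 3. Two single cases**
- Raw 480 ms at 50 bpm gives QTcF 452 and QTcB 438. Removal is mandatory.
- Raw 440 ms at 80 bpm gives QTcF 484 and QTcB 508. The numeric limit is not met.

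**Step 4. Does the formula matter?** Both formulas show the error in the same directions, but at 75 bpm raw 470 ms is 506 ms by Fridericia and 525 ms by Bazett. Writing QTc alone would leave a gap of about 19 ms at that rate.

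The number of subjects affected among 32 cannot be computed, because the documents give no distribution of heart rate or QT.

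**The case against.** The strongest reply is that QT is shorthand for the corrected value. The protocol never says uncorrected, and 470 ms could be read as a corrected limit. If so, the defect is a missing word and a missing formula name, and the bands above arise only if staff apply the text to raw QT. This may be what the authors meant, but the documents do not say so. Even on that reading, the formula has to be named.

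Second, the faster-rate case is not unprotected. The second limb is equally mandatory once a change is judged clinically meaningful, cardiac symptoms are a separate stopping ground, and section K lets the investigator withdraw subjects for safety. This stands: such cases are left to judgement rather than missed outright. None of it helps in the slow-rate case, where the numeric limb leaves no discretion.

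Third, screening and pre-dose ECGs narrow the slow-rate problem. They do so only in part, because entry has no QT limit. A pre-dose exclusion would also come after randomization.

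Fourth, any Day 0 stop falls outside the intention-to-treat population, however well the trigger is specified, and no bias between arms is shown. That is right: correcting the QT would not change the population definition. The loss is still a real consequence of each unnecessary removal. Section K and the glucose provisions let subjects stop pills and stay in follow-up, but the ECG rule ends participation in the study and makes no such provision.

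Fifth, events should be rare at 100 mg. This bears on how serious the point is, not on whether the rule is correct.

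**Conclusion.** The concern holds. As written, the stopping limit is a raw QT of 470 ms, which matches a corrected limit of 470 ms only at 60 bpm. With Fridericia correction the mismatch is about 29 ms at 50 bpm (removals that a corrected limit would not require) and about 34 ms at 75 bpm (long corrected values outside the numeric limit). Those widths rest on the assumed heart rates, on the Fridericia formula, on 470 ms being the intended corrected limit, and on literal application of the text. The existence and direction of the error do not depend on which of the two formulas is used.

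The expected frequency is low and no effect on the primary comparison is shown. The point should still be fixed, because it concerns the plan's only numeric cardiac safety trigger and the correction is simple.

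**What to change.** In Stopping rules, state the limit as a heart-rate-corrected QT with one named formula: for example, end participation if QTcF exceeds 470 ms at 1 or 4 hours after the first dose, or another corrected limit that the sponsor sets. If the authors already meant a corrected value, say so and name the formula.

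In section C, apply the same corrected measure to the screening and pre-dose ECGs, so that eligibility and stopping rest on one quantity. At screening this acts before randomization.

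The cost is one sentence in Stopping rules and a matching phrase in the exclusion criteria. No extra ECG, visit or staff is needed. Heart rate must be recorded with each tracing; the ECG form is not in the documents, so whether it already is cannot be told.

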
Schedule of activities

After a single visit screening process, eligible subjects will be enrolled in this study for 12 months each. They will visit the HNRCA as follows: 1) enrollment visit - sign consent form, receive oral D₃-creatine dose, and have practice leg endurance measurement; 2) baseline visit – medical history and physical measures, DXA scans, blood draw, pill dispensing and receive first drug dose, and have pre-dose, 1-hr post first dose, and 4-hr post first dose ECGs (ECGs this visit only); 3) 2 mo visit – repeat baseline measures (except D₃-creatine), pill count; 4) 6 mo visit – repeat baseline measures (except D₃-creatine), pill count; 5) 3 days prior to final 12 mo visit – receive oral D₃-creatine dose; 6) 12 mo visit – repeat baseline measures and pill count. Additionally, subjects will be called at 4, 8, and 10 mo to reinforce pill compliance and to answer any questions they may have.

INTRODUCTION

Rationale This study is an initial evaluation of the effectiveness of the novel ghrelin receptor agonist, anamorelin, on increasing muscle mass, strength, and function and enhancing bone formation in men and postmenopausal women with low bone and muscle mass (osteosarcopenia, OS). Anamorelin has been tested in normal adults and in patients with cancer cachexia but it has not been tested in patients with osteopenia, sarcopenia, or OS.

Background Osteopenia and sarcopenia result from the age-related losses of bone and muscle mass that occur at about 1-2% per year after age 50 years (1-3). Muscle strength declines more rapidly than muscle mass (4-6), nonetheless the loss of muscle mass is a major factor in the decline in strength that occurs with aging (7-10). The definition of osteopenia is standardized, and refers to a BMD T-score of -1 to -2.5. Currently there is no standardized definition of sarcopenia. Mounting recent evidence indicates that lower levels of functional measures, grip strength and gait speed, are significant predictors of falls and hospitalizations,

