ECGs before and 1 & 4 hr post dose		X					^e DXA total body scans at 2, 6, &12 mo; spine and non-dominant hip scans at 12 mo (screening scans will serve as baseline)
Diet assessment ^a		X				X	^f Serum P1NP at 0, 2, 6, and 12 mo; serum IGF-1 and CTX at 0 and 12 mo; serum 25(OH)D at 0 and mo 6; and alpha-acid glycoprotein at visit 0; archive 4 aliquots serum and 1 of plasma at 0 and 12 mo.
Questionnaires ^b		X		X		X	^g Safety monitoring: fasting plasma glucose & serum AST/ALT at 0, 2, 6, and 12 mo; symptoms and other AEs documented
Muscle strength ^c	X	X	X	X		X	^h By pill diary and counting returned pills
Muscle perform. ^d		X	X	X		X	ⁱ Administer 60-mg oral dose of D ₃ -creatine
DXA scans ^e			X	X		X	^j Collect fasting spot urine for D ₃ -creatine dilution determination
Study blood ^f		X	X	X		X	
Dispense pills		X	X	X			
Safety measures ^g		X	X	X		X	
Adherence ^h			X	X		X	
D ₃ -creatine dosing ⁱ	X				X		
Fasting spot urine ^j		X				X	
Waist circumference						X	

In addition to the above study visits, we will contact participants by telephone at 4, 8, and 10 months to determine whether they have any study related concerns and to remind them of the importance of taking one study pill per day. The content of these calls will be documented on the Call/comment Log.

C. Inclusion and exclusion criteria

Inclusion criteria: Ability to sign informed consent form; community dwelling men (who are sterile or agree to use contraception throughout the study) and postmenopausal women (no menses for 5 years; early postmenopausal women are ineligible because their bone turnover rate is changing rapidly); age 50 years and older; sarcopenia defined as maximum grip strength <35.5 kg (men) and <20 kg (women) in either hand (excluding hands with severe pain or recent surgery) and/or gait speed <0.8 m/sec (11); osteopenia defined as spine (at L1, L2, L3, or L4) or non-dominant total hip or femoral neck BMD T-score between -1.0 and -2.5; mini-mental state examination (MMSE) score >21.

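### The in-study stop rule omits non-antiarrhythmic drugs that may prolong PR or QRS, and it ends participation where stopping the pills would keep the month-12 primary measure

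*Combined protocol and SAP*

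**What the plan says.** **Entry.** The medication exclusions in section C include "use of drugs that may prolong the PR or QRS interval durations, such as any of the Class I/Sodium" channel blockers. This class is defined by its effect on conduction, and the named agents illustrate it. The same list bars "drugs with high affinity to AAG and therefore with potential to displace anamorelin from binding (e.g., carvedilol, chlorpromazine") and "inhibitors of P-glycoprotein (e.g., verapamil, quinidine), and inhibitors of OATP1B3 (e.g., cyclosporine, rifampicin"), together with five named strong CYP3A4 inhibitors.

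**During treatment.** Under Stopping rules, participation ends "if he/she is prescribed the following drugs during the study". Five lines follow. The conduction line reads "Channel blocking antiarrhythmic medication (flecainide, procainamide, propafenone, quinidine"). The lines for AAG, P-glycoprotein and OATP1B3 repeat the entry labels and the same drugs but do not mark the drugs as examples. The CYP3A4 line names the same five drugs as at entry.

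**ECGs.** Apart from the screening ECG, the narrative schedule has subjects "have pre-dose, 1-hr post first dose, and 4-hr post first dose ECGs (ECGs this visit only"). The table in section B agrees: its row "ECGs before and 1 & 4 hr post dose" is marked at the baseline visit alone. The ECG stop rule applies to a QT above 470 ms or "if other clinically meaningful ECG changes occur at either 1 hr or 4-hrs post first dose".

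**Leaving treatment or the study.** Section K reserves permanent off-study status for withdrawal of consent, lets the investigator withdraw a subject for safety, and allows a subject to be off pills and still attend visits. Under Protection against risks, a repeated fasting glucose of 200 mg/dl or more stops the pills while measurements continue. Stopping rules, by contrast, ends participation for the same glucose finding.

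**The concern.** The reason for barring conduction-slowing drugs at entry applies throughout 12 months of dosing. If the in-study rule covers less than the entry rule, a drug that would have kept someone out can be started after randomisation with no required response. Scheduled ECGs stop after the first-dose visit, so no planned ECG would show a later change.

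The action raises a second, separate question. The primary measure needs D₃-creatine values at baseline and at month 12, and it is taken at no other time. A subject whose participation ends in between has no primary change score. The data analysis section describes a two-sample t-test on the 12-month change and gives no method for a missing month-12 value. Subjects lost this way are selected by an event after randomisation, namely a new prescription.

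**Working it through.** **1. Entry rule against in-study rule, class by class**

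| Class | Entry (section C) | Stopping rules | Difference |
|---|---|---|---|
| PR/QRS-prolonging drugs | Defined by effect; Class I agents as examples | Channel-blocking antiarrhythmics, four named | Non-antiarrhythmic members drop out; the Class I limit also drops out |
| High-affinity AAG binders | Class, two examples | Same label, same two drugs | Example marker missing |
| P-glycoprotein inhibitors | Class, two examples | Same label, same two drugs | Example marker missing |
| OATP1B3 inhibitors | Class, two examples | Same label, same two drugs | Example marker missing |
| CYP3A4 inhibitors | Five named drugs | Same five | Only the word strong is dropped |

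Entries in the stop rule: 5 + 4 + 2 + 2 + 2 = 15. Quinidine appears twice, so there are 14 distinct drugs. Only the first row changes what the rule covers. Protection against risks still marks the AAG, P-glycoprotein and OATP1B3 drugs as examples, so the missing marker in those three lines is a drafting detail.

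**2. What would catch a drug in the gap**

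- Participants are told to report a new prescription before taking its first dose (Protection against risks).
- The follow-up history at each later visit covers recent medication use (section F), and calls at 4, 8 and 10 months ask about study concerns (section B).
- Cardiac symptoms end participation, and the investigator may withdraw a subject for safety (Stopping rules; section K).

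The drug is therefore likely to come to the investigator's notice. What is missing is a stated response.

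**3. What the two actions do**

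Ending participation and stopping the pills both end exposure to the study drug, so they do not differ on that score. They differ in whether the subject returns for the day-361 dose and the month-12 urine sample.

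**4. How much room there is for lost primary values**

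Inputs: SD of change 1.84 kg, difference 2.28 kg and 12 per group (section I); 32 enrolled and 24 completers (section A). Two-sided alpha of 0.05 is assumed, because the 0.05 level is stated under the secondary aims without sidedness. No power is stated for the primary, so 80% is assumed.

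- Plan's figure: SE = 1.84 × √(1/12 + 1/12) = 0.751 kg. Noncentrality = 2.28 / 0.751 = 3.04 on 22 df, which gives power of 82.7%. The difference detectable with 80% power is 2.20 kg, below 2.28, so the plan's statement is reproduced.
- Allowed losses: 32 − 24 = 8, or 25%; 24 / (1 − 0.25) = 32.
- Fewer completers than planned: 12 + 11 gives 80.8%, 11 + 11 gives 78.9%, and 12 + 10 gives 78.6%.

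These lower figures apply only if the other losses have already used up the allowance of 8.

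- Cost of retention: suppose one of 12 anamorelin subjects stops pills early and keeps none of the effect. The expected difference becomes 2.28 × 11/12 = 2.09 kg. That is below 2.20, so power falls under 80%, against 80.8% if that subject is simply lost. A pill stop in the placebo group dilutes nothing, and a late stop on active drug would be expected to dilute less.

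Retention therefore protects the completeness of the randomised comparison. It does not reliably add power.

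**The case against.** The strongest reply is that no drug in the gap can be named from the documents. Section C's only PR/QRS examples are the four drugs that the stop rule also names, and no prescribing rate is given. Reporting and medication review already bring new drugs to a physician, and a mandatory list backed by clinical judgement is a defensible design. The protocol also reports PR and QRS increases at 300 mg/d but no clinically meaningful effect at 100 mg, the trial dose. All of this stands and keeps the point small. It does not explain why an effect-defined class at entry should become a class of antiarrhythmics afterwards.

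It is also fair to say that the in-study line is not narrower in every respect. By dropping the Class I limit, it could reach channel-blocking antiarrhythmics of other classes. The gap is confined to non-antiarrhythmic drugs.

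A reader might infer that all four open classes have been closed to the named drugs. The documents do not support that for AAG, P-glycoprotein and OATP1B3: each line keeps its class label, and the adjoining safety text presents the drugs as examples.

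A reader might also infer that the pill-stop action makes subjects safer. It does not, because exposure ends either way. Finally, a mandatory stop for an open class has no stated upper limit on how often it would apply. That objection stands, and it is a cost of the change.

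**Conclusion.** Two minor points hold. First, the in-study rule requires no action for a non-antiarrhythmic drug that may prolong PR or QRS and is not named elsewhere in the rule, although such a drug is barred at entry. Second, ending participation for a prohibited drug gives up the month-12 primary value, although the protocol already has a pill-stop route that would keep it.

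The number of subjects affected by either point cannot be computed and is probably small among 32. Neither point changes alpha, the sample size or the planned power.

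A reader might go further and see an unprotected cardiac hazard. Advance reporting, medication review, the symptom rule, the investigator's discretion and the reported absence of a meaningful effect at 100 mg all argue against that. The conclusion on the first point rests on reading the conduction line as a class of antiarrhythmics. If it is read as only the four named drugs, the gap is wider.

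**What to change.** Under Stopping rules:

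1. Replace the channel-blocker line with section C's class, defined by possible prolongation of PR or QRS, and give the four named drugs as examples. Use the same class when new prescriptions are checked. Which other drugs belong to it is for the sponsor's clinicians to list.
2. For every listed prohibited drug, the CYP3A4 inhibitors included, change the action to stopping study pills and continuing scheduled follow-up through the month-12 D₃-creatine measurement. State whether pills may resume after a short course; the adverse-event reporting section already recognises temporary discontinuation. Keep the investigator's right to withdraw a subject for safety.
3. As an editorial matter only, mark the drugs in the AAG, P-glycoprotein and OATP1B3 lines as examples.

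The cost is protocol wording and an updated medication checklist, with no added visit, ECG, test or participant. The downside is possibly some more pill stops, number unknown, and some dilution of the intention-to-treat contrast when a subject on anamorelin is followed off treatment.
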